10.0 Withdrawal of Subjects*

Subjects will be withdrawn from the research without their consent if they do not return for the scheduled 3 month post-operative visit. In this case, subjects will be notified that they can no longer participate and their insurance billed for the cost of the onabotulinumtoxinA used during the procedure, with the subject covering any cost not covered by insurance.

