5.0 Study Endpoints

Primary endpoint will occur at 3 months. Secondary endpoint is at 1 year, or when the subject completes her 1 year post-operative visit.

6.0 **Procedures Involved**

Women with MUI undergoing midurethral sling for bothersome SUI will be randomized to 100 units onabotulinumtoxinA or placebo (saline) injections in the detrusor at the time of sling surgery. Specifically, the retropubic midurethral slings used will be either the Gynecare TVT Exact Continence System by Ethicon or the Boston Scientific Advantage Fit Transvaginal Mid-Urethral Sling System based on surgeon preference. Surgeons and participants will be masked to study assignment. Primary outcome will be the Patient Global Assessment of Improvement (PGI-I), a global, patient oriented measure that assesses symptoms of SUI and UUI at 3-months. The primary outcome, PGI-I asks subjects to best describe how their urinary tract condition is now, compared to how it was before treatment for urinary leakage. Response choices are: (1) 'very much better', (2) 'much better', (3) 'a little better', (4) 'no change', (5) 'a little worse', (6) 'much worse', and (7) 'very much worse'. Construct validity of the PGI-I was demonstrated in incontinence trials.32

We selected a subjective, patient oriented outcome as our primary outcome measure secondary to the complex nature of MUI, and the association between dissatisfaction after incontinence surgery and persistent or new onset urgency. We felt the patient's overall impression of their continence status represented a more clinically meaningful outcome than traditional objective measures. In addition, we will compare subjective and objective urinary symptoms and quality of life amongst treatment groups 3-months and 1-year after surgery.

All women with MUI planning surgical intervention with midurethral sling will be approached for study participation. MUI will be defined as an answer of "moderately' or "quite a bit" bothered to Urinary Distress Inventory (UDI) items (2) "urine leakage with a feeling of urgency" AND (3) "urine leakage related to coughing, sneezing, or laughing".

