Women will undergo standardized urologic evaluation at baseline including assessment of urinary symptoms and quality of life using short forms of the Urinary Distress Inventory (UDI-6) and Incontinence Impact Questionnaire (IIQ-7); assessment of overall severity of their incontinence symptoms with the Patient Global Impression of Severity (PGI-S);32 post void residual urine volume; urine analysis and culture; multichannel urodynamic testing; and pelvic exam with prolapse quantification using pelvic organ prolapse quantification system (POP-Q)33. All patients will also complete a 3-day urinary diary at baseline quantifying the number of incontinence episodes (stress and urge). Three months and 1-year after surgery, patients will again complete all baseline measures, including UDI, IIQ, PGI-I, PGI-S, and 3-day diary to report symptom and objective urinary symptoms after treatment. A sample of urine will be obtained for microbiome analysis at each visit.

Scheduled in-person follow-up visits will occur at baseline, 2 and 6-weeks, 3-months, and 1-year after surgery. At the baseline, 3-month, and 1-year visits,

 $PROTOCOL \ TITLE: \ \text{The SLIM Study: } \underline{Sl} \text{ing and Botox} \\ \textcircled{B} \ \underline{Injection for \ \underline{M} ixed \ Urinary \ Incontinence}$

research staff will collect the 3-day diary information and record any adverse events that have occurred during the post-operative period. Subjects will also complete the general and condition specific symptom and QOL questionnaires. In addition, an update of current medication and assessment as to whether any evaluation or treatment for pelvic floor disorders or adverse outcomes from surgery have occurred since the previous evaluation will be assessed by clinical staff at the in-person visits. All patient and survey data will be recorded in RedCAP.

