9.0 Provisions to Monitor the Data to Ensure the Safety of Subjects

Adverse events associated with midurethral sling surgery in conjunction with onabotulinumtoxinA injection will be recorded, but only include events such as post-operative urinary retention requiring catheterization, post-operative urinary tract infection, and persistent urinary urgency. Adverse events will be recorded at each follow up visit on Case Report Forms and subsequently will be added in to REDCap electronic data capture system. The PI will be notified of any adverse events, which will be resolved with the patient.

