14.0 Setting

Research will be conducted in Northwestern Medical Group's outpatient clinic, the Integrated Pelvic Health Program (IPHP). Potential subjects will be identified and recruited by physicians within the practice. Once potential subjects are identified, the study coordinator will provide the patient with information about the study. If the patient is interested in joining the study, the study coordinator will consent the patient in the IPHP clinic. The patients will complete questionnaires per the study either at home or in the clinic in a private room. Demographic and medical and surgical data will be collected from the patient's medical record and recorded on the RedCAP secure server. $PROTOCOL \ TITLE: \ \text{The SLIM Study: } \underline{Sl} \text{ing and Botox} \\ \textcircled{B} \ \underline{Injection for } \underline{M} \text{ixed Urinary Incontinence}$

After consenting to the study, the surgical procedure that subjects are undergoing as part of their standard of care will be performed at an NMHC facility. The onabotulinumtoxinA injections will be performed in the operating room by one of the study physicians. Randomization will be performed via RedCAP on a secure online server through a hospital computer.

The subjects post-operative visits will take place in the Integrated Pelvic Health program, and NMHC outpatient clinic, as part of standard of care. Additional questionnaires will be completed at these visits and data will be collected from these visits as well.

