20.0 Economic Burden to Subjects

Because these patients will already be undergoing retropubic midurethral sling as an inclusion criterion for participation in this study, each participant would already be incurring the costs of visits, parking, all pre-operative and postoperative testing, and operating room fees. There are no additional tests or visits required as part of this study. All onabotulinumtoxinA used and placebo saline in addition to syringes and needles will be covered in the study budget and not incurred by the patient or the patient's insurance.

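### Section 10.0 withdraws any randomised woman who misses the 3-month visit, losing primary and 1-year data that could still be collected, and its billing clause contradicts Section 20.0

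*Protocol*

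**What the plan says.** Protocol Section 10.0: "Subjects will be withdrawn from the research without their consent if they do not return for the scheduled 3 month post-operative visit". In that case "subjects will be notified that they can no longer participate", with "their insurance billed for the cost of the onabotulinumtoxinA used during the procedure, with the subject covering any cost not covered by insurance". No window, grace period or continued follow-up is described.

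Section 5.0 sets the timing of the endpoints: "Primary endpoint will occur at 3 months. Secondary endpoint is at 1 year, or when the subject completes her 1 year post-operative visit". Section 6.0 gives the visit schedule: "Scheduled in-person follow-up visits will occur at baseline, 2 and 6-weeks, 3-months, and 1-year after surgery". It also has PGI-I and the other questionnaires completed at 3 months and again at 1 year. Section 14.0 allows completion away from the clinic: "The patients will complete questionnaires per the study either at home or in the clinic in a private room". On safety, Section 9.0 says: "Adverse events will be recorded at each follow up visit on Case Report Forms".

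On cost, Section 20.0 says the onabotulinumtoxinA and the placebo saline "will be covered in the study budget and not incurred by the patient" or by her insurer, and it states no exception.

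Section 8.0 names a chi-square test for dichotomised PGI-I. The SAP lists tests and assumes 15% dropout. Neither document defines an analysis population or says how a missing PGI-I is handled.

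**The concern.** The rule is triggered at the one visit where the primary outcome is due. Read as written, a missed appointment does three things:

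- It ends participation before a late or home-completed PGI-I can be obtained, although PGI-I is a single self-reported item.
- It bars the woman from the 1-year endpoint.
- It stops research recording of adverse events from that point. Events recorded at 2 and 6 weeks are unaffected.

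The rule does not itself remove her from the analysis. With no stated population or missing-data method, however, a chi-square test on available PGI-I is a returners-only comparison. Whether a woman returns may depend on her outcome in either direction: dry and no longer bothered, or dissatisfied and seeking care elsewhere. It may also differ by arm. Randomisation does not protect that comparison.

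The payment clause is a separate contradiction, mainly of cost and ethics. Only the active arm has onabotulinumtoxinA to bill, so a bill could reveal assignment despite the masking in Section 23.0.

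**Working it through.** **Inputs.** From the SAP: 66% improved on placebo and 93% on onabotulinumtoxinA, 34 per arm needed, 80% power, alpha 0.05, 15% dropout, 78 recruited (39 per arm). From Protocol Section 8.0: about 100 recruited (50 per arm), attrition rate not given.

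**The plan's own figure.** Two-sided, pooled variance, no continuity correction:

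n = [1.96·√(2·0.795·0.205) + 0.8416·√(0.66·0.34 + 0.93·0.07)]² / 0.27² = 33.9, so 34 per arm (power 80.1%).

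The SAP's 78 matches 68 × 1.15 = 78.2; dividing instead gives 68/0.85 = 80. At 15% loss, 39 per arm leaves 33.15 and power of 79.1%. Power is therefore a minor matter, and the issue is bias.

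**Bias with no true effect, selective loss in one arm.** Assumptions not in the documents: all 15% is lost at month 3, the true rate is 66% in both arms, and one group is lost at k = 2 or 3 times the rate of the other. Let L = 0.15.

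- Non-improvers lost more: r = L/(0.66 + 0.34k); observed rate = 0.66(1 − r)/(1 − L). For k = 2: r = 0.15/1.34 = 0.1119, observed 0.66 × 0.8881/0.85 = 0.6896.
- Improvers lost more: r = L/(0.66k + 0.34); observed rate = 0.66(1 − kr)/(1 − L). For k = 2: r = 0.15/1.66 = 0.0904, observed 0.6361.

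Rejection rates are by exact enumeration of the uncorrected chi-square against 66%.

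| Lost more | k | Observed | Bias (points) | Rejection, 33 per arm | Rejection, 42 per arm |
|---|---|---|---|---|---|
| Neither | 1 | 66.0% | 0 | 5.4% | 5.2% |
| Non-improvers | 2 | 69.0% | +3.0 | 6.1% | 6.1% |
| Non-improvers | 3 | 70.7% | +4.7 | 7.3% | 7.6% |
| Improvers | 2 | 63.6% | -2.4 | 6.0% | 5.9% |
| Improvers | 3 | 62.6% | -3.4 | 6.6% | 6.7% |

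**The rule's own share.** Some loss would occur without the rule. If half of the missed women could be reached (assumed), L = 0.075 with 36 per arm. The bias becomes +1.36, +2.17, -1.10 and -1.57 points, and rejection is 5.5% to 5.8%. The share due to the rule is the difference in size: 2.96 − 1.36 = 1.60; 4.71 − 2.17 = 2.54; 2.39 − 1.10 = 1.29; 3.41 − 1.57 = 1.84 points.

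**Equal selection in both arms.** With no effect there is no bias. At 93% vs 66% the 27.0-point difference becomes 25.1 or 24.3 (non-improvers lost more, k = 2 or 3), or 28.8 or 29.6 (improvers lost more).

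**Tipping point, no selection model.** Take returners at about the planned rates with 6 missing per arm: 31/33 vs 22/33, p = 0.005.

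- All missing counted as not improved: 31/39 vs 22/39, p = 0.029.
- 0 of 6 active and 2 of 6 placebo improved: 31/39 vs 24/39, p = 0.082.
- 0 of 6 active and 6 of 6 placebo improved: 31/39 vs 28/39, p = 0.43.
- p exceeds 0.05 in 14 of the 7 × 7 = 49 possible patterns.
- With only 3 missing per arm: 3 of 16 patterns (33/36 vs 24/36) or 1 of 16 (34/36 vs 24/36).

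These are counts of patterns, not probabilities.

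**Women barred from 1 year,** if all dropout is at month 3: 0.15 × 78 = 11.7, or 0.15 × 100 = 15.

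**Payment.** Section 10.0 charges the drug to insurer and then subject. Section 20.0 says neither incurs it. Both cannot hold.

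**The case against.** The strongest reply is that the harm belonging to the rule is small and rests on assumptions. Section 15.0 expects good return because the visits are standard care, dropout is already allowed for, and power barely moves. The rule's share of 1.3 to 2.5 points needs four inputs that the documents do not give: the selection ratio, one-arm selection, all loss at month 3, and half the women reachable. This stands, and the figures should be read as illustrations.

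The inflated rejection rates also depend on the test version. With a continuity correction, 33 per arm gives 2.8% with no selection and 3.2% to 3.9% in the four one-arm scenarios, all below 5%. That stands too, although the planned 34 per arm reproduces only without the correction. The bias in the estimate does not depend on the test.

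The tipping count can overstate fragility. In all 14 patterns the missing placebo women improve by at least 2 of 6 more than the missing active women, against the planned effect. If non-improvers are lost 2 or 3 times as often in both arms at the planned rates, those patterns have probability 0.4% to 0.5%. If missing women in both arms improve at 66%, it is about 15%.

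With no window stated, a rescheduled visit might count as returning, and Section 14.0 does not say that home completion replaces an attended visit. The strict reading is therefore not the only one, but no clause preserves follow-up for a woman who does not return. The adverse-event loss is mainly the 1-year record. A bill reveals nothing that affects data while billed women are already out; it matters once they are kept in.

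None of this defends the rule or resolves the payment conflict.

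**Conclusion.** The concern holds and should be fixed. The rule turns 3-month and 1-year outcomes that might be retrieved into permanent loss, and the payment clauses contradict each other. The size and direction of the bias are unknown. Under the stated assumptions it is a few percentage points either way, with only part of that due to the rule. Confidence in the size is moderate at best. The loss of follow-up and the payment contradiction rest on the text alone and need no modelling.

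**What to change.** - Delete the forced-withdrawal sentence, so that a missed visit is not a withdrawal.
- Keep these women enrolled. Seek PGI-I and the questionnaires by home, mail or phone completion within a stated window, recording date and mode, and continue 1-year and adverse-event follow-up.
- Define the primary analysis as women as randomised, using every PGI-I obtained. Add a tipping-point analysis that varies the outcome of still-missing women separately by arm and in both directions. Counting missing as not improved is not enough alone: in the example it keeps p = 0.029 and hides the patterns where significance is lost.
- Reconcile Sections 10.0 and 20.0 on payment so that no bill reveals the arm.

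The cost is a short amendment and about 12 women to contact (15% of 78) or 15 (15% of 100), some more than once, with slightly mixed modes of collection. No extra patients or visits are needed, and Section 20.0 already places the drug cost in the study budget.

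The SAP is written in the past tense. If follow-up is complete, apply the analysis part only, report missing PGI-I and Section 10.0 withdrawals by arm, and settle the payment conflict. For the statistics, that costs only analysis time.

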11.0 Risks to Subjects*

Risks associated with the project are minimal. Patients participating in the project will already be undergoing a retropubic midurethral sling for bothersome stress

 $PROTOCOL \ TITLE: \ \text{The SLIM Study: } \underline{Sl} \text{ing and Botox} \\ \textcircled{M} \ \underline{Injection for } \underline{M} \text{ixed Urinary Incontinence}$

urinary incontinence, and will already have been counseled on and have understood the risks associated with that surgical procedure. None of the risks associated with that surgical procedure will change (increase or decrease) by participating in this study.

This additional risks associated with the procedure are for the patients in the onabotulinumtoxinA arm. Intravesical injection incurs a 5% increased risk of urinary retention requiring clean intermittent self catheterization. All patients will be taught this technique prior to the procedure regardless of study arm. Those with urinary retention have an increased risk of urinary tract infection. This is time-limited and last for less than 2 months on average. All patients will be informed of these risks as part of the consent process.

Another risk to subjects is that we will be collecting their personal health information in a database. All of the data will be kept confidential and will be stored on password protected, secure servers, or in locked cabinet files that only study staff on the project have access to. Personal health information will be stored on files that are separate from the subject's name, all health information will be coded. Coded list will be kept on secure, password protected file.

12.0 Potential Benefits to Subjects

Given the superior efficacy and side effect profile of onabotulinumtoxinA and the high rates of persistent urgency incontinence and dissatisfaction after sling surgery in women with MUI, we hypothesize that a combined treatment approach for women with MUI is superior to simply treating the stress incontinence alone. Specifically, women with MUI undergoing sling plus intradetrusor onabotulinumtoxinA will have fewer bothersome incontinence symptoms than women undergoing sling alone. It is possible that subjects will have significant improvement in quality of life due to the improvement in urinary symptoms that they would not have been offered without this study.

13.0 Sharing of Results with Subjects

Results will not be directly shared with subjects

14.0 Setting

Research will be conducted in Northwestern Medical Group's outpatient clinic, the Integrated Pelvic Health Program (IPHP). Potential subjects will be identified and recruited by physicians within the practice. Once potential subjects are identified, the study coordinator will provide the patient with information about the study. If the patient is interested in joining the study, the study coordinator will consent the patient in the IPHP clinic. The patients will complete questionnaires per the study either at home or in the clinic in a private room. Demographic and medical and surgical data will be collected from the patient's medical record and recorded on the RedCAP secure server. $PROTOCOL \ TITLE: \ \text{The SLIM Study: } \underline{Sl} \text{ing and Botox} \\ \textcircled{B} \ \underline{Injection for } \underline{M} \text{ixed Urinary Incontinence}$

After consenting to the study, the surgical procedure that subjects are undergoing as part of their standard of care will be performed at an NMHC facility. The onabotulinumtoxinA injections will be performed in the operating room by one of the study physicians. Randomization will be performed via RedCAP on a secure online server through a hospital computer.

The subjects post-operative visits will take place in the Integrated Pelvic Health program, and NMHC outpatient clinic, as part of standard of care. Additional questionnaires will be completed at these visits and data will be collected from these visits as well.

15.0 Resources Available

The staff that will be involved in this research are highly qualified. The Principle Investigator, [name], is the chief of Female Pelvic Medicine and Reconstructive Surgery and is nationally and internationally recognized for research in pelvic floor disorders and has served as primary investigator on many studies funded by the National Institute of Health. She has authored or coauthored 150 scientific papers and currently serves on the editorial board of Obstetrics & Gynecology and the Journal of Female Pelvic Medicine & Reconstructive Surgery. The other study physicians assisting in recruiting efforts have completed their fellowships in Female Pelvic Medicine & Reconstructive surgery and are both involved in numerous research studies and serve as reviewers for several scientific journals. The nurse practitioner on staff at the IPHP has worked on several other protocols during her time at Northwestern. The study coordinator on staff has over 3 years of research experience and 1 year of experience working in clinical trials and consenting patients.

Due to the high volume of patients that present with mixed urinary incontinence in our clinic, it is feasible that the required number of suitable subjects will be recruited within the estimated window of time. Also, since study participants are undergoing surgery as part of standard of care, they will be more likely to return for their follow-up visits since these are part of their standard post-operative care. Our center will begin enrolling participants once we have IRB approval, tentatively July 2015. With the time required recruit 100 patients (approximately two years), collect outcomes data on the enrolled subjects for a year, and analyze data, this study will be active until June 2018.

The Integrated Pelvic Health Program, affiliated with Northwestern Memorial Hospital, helps individuals with pelvic floor disorders. It is the only program in the Chicago area that brings together a multispecialty approach to pelvic floor disorders in one location. Our dedicated team of physicians, nurses, and physical therapists are committed to restoring the quality of life for people with such disorders. Both the physicians and the facilities offer state-of-the-art resources to ensure the highest quality evaluation, medical and surgical care to women with incontinence and prolapsed. Our physicians are national leaders in minimally

invasive pelvic reconstructive surgery and sacral nerve stimulation for urinary and fecal incontinence.

All study staff members are in possession of the protocol and the protocol has been reviewed by all of the study members during a research conference. Research procedures have been made clear and were outlined by the study coordinator and Principle Investigator.

16.0 Recruitment Methods

Subjects with mixed urinary incontinence already undergoing retropubic midurethral sling for bothersome stress urinary incontinence will be identified at the Integrated Pelvic Health Program, and Northwestern Medicine. Once potential subjects are identified, the study coordinator will provide the patient with information about the study.

The source of the subjects will be those women meeting criteria for mixed urinary incontinence who are already undergoing a retropubic midurethral sling for bothersome stress urinary incontinence with one of the providers at the Integrated Pelvic Health Program affiliated with Northwestern Medicine.

17.0 Local Number of Subjects

This is a single center study at Northwestern Medicine. We will require up to 100 participants to meet power requirements for this study while appropriately accounting for attrition rate.

